6.6.1.4 Observed cases - Off Treatment (OC-OffT) analysis

6.6.1.5 Last observation carried forward (LOCF)

An alternative method for quantitative endpoints is to replace missing values of a patient by his/her last observed measurement on-treatment.

The last observation on-treatment need not necessarily be a value selected as a visit value if multiple measurements were performed within a time window for a visit. In this case the last on-treatment value within the time window will be carried forward, while the visit value can be the value that was observed closest to the planned visit date or the first value observed in the time window. See [Table 6.7: 2](#) for further details.

Missing values within a course of measurements on-treatment will be interpolated based on the last observed value before the missing visit and the first observed value after the missing visit. This is independent from the selection of a value as the picked visit value to be used in the descriptive analysis by visit (as described in [Section 6.7](#)).

Let:

D0 = date of a visit with a missing endpoint value;

D1 = date of the next visit (with endpoint value non-missing) after the visit with missing endpoint;

D-1 = date of the previous visit (with endpoint value non-missing) before the visit with missing endpoint;

E_i = endpoint values for visits D_i for i= -1, 0 and 1

Then the missing endpoint value can be interpolated as:

$$E_0 = E_{-1} + ((E_1 - E_{-1}) \times (D_0 - D_{-1}) / (D_1 - D_{-1})).$$

Missing data will only be imputed up to the planned visit to be reached by all randomised patients (week 26).

If there are no on-treatment measurements, the value from pre-treatment or baseline will not be carried forward to populate the missing on-treatment values according to the FAS definition.

6.6.1.6 Multiple imputation (MI)

A multiple imputation approach will be used as a sensitivity analysis for the primary endpoint. Further details can be found in [Section 7.4.2](#).

6.6.1.7 Non-completers considered failure (NCF)

For binary endpoints, like the occurrence of a response, a conservative method to replace missing values is to consider them as "failures". Off-treatment values will be set to missing. Missing data due to early discontinuation of treatment per the completer definition will be replaced as "failure" (e.g. non-responder) up to the planned timepoint for the analysis.

6.6.2 Safety and other variables

Missing safety data will not be replaced.

An analysis of the changes from baseline to the last available value under treatment and the minimum and maximum post baseline will be determined for quantitative safety laboratory variables.

6.6.3 Missing dates and times

Missing or incomplete AE dates are imputed according to BI standards (see “Handling of missing and incomplete AE dates”) (6).

If the date of first drug administration is missing but the patient was randomised, the date of the first drug administration will be set to the date of randomisation. If the date of first administration is partially missing with the month and year present, the day will be set to the date of randomisation if randomisation was in the same month. If randomisation was in the month prior to the first drug administration the missing day will be imputed as the first day of the month.

A missing time of first drug administration will be imputed as 08:00 o'clock in the morning, missing administration times at on-treatment visits will be imputed by 08:00 o'clock in the morning.

As a general rule a missing drug stop date will be imputed according to the following principles:

- If an End of Treatment (EoT) visit or visit 11 is documented, it should be the date of the EoT visit.
- If the date is incomplete with only month and year and the EoT visit is missing, it should be the first day of the following month.
- If the patient is lost to follow-up it should be the date of the last visit + the longest treatment duration based on drug supply + 1 day.
- If a patient died during the course of the trial and no additional information about drug stop date are available, the date of death will be used as drug stop date assuming that the patient took the medication until the day of death.
- All other cases need to be assessed by the trial team on an individual basis, trying to use the points above as guidance.

If only the year of birth is known, the day and month of birth will be imputed as 01 January.

For partial start and stop dates for concomitant therapies (CT) the following derivations will be used to impute 'worst case' values:

- If the day of the end date is missing then the end date is set to last day of the month.
- If the day and month of the end date are missing then end date is set to 31st December of the year.
- If the day of the start date is missing the start date is set to first day of the month.
- If the day and month of the start date are missing then the start date is set to 1st January of the year.

For other incomplete date information (except to assess the overall compliance, see below) always the midpoint of the possible interval will be used. If only the year is present the day and month will be imputed as 01 July, if year and month is present the day will be imputed as 15. If the year is missing, the date will be considered missing.

In case of missing visit date for a compliance record, the following hierarchy will be used to select a date to impute the missing visit date:

- The visit date registered in the IRT system
- The date of the vital sign measurement
- The date of the safety laboratory sampling
- The start date of the CGM period (only applicable to Visit 11)

All other cases need to be assessed by the trial team on an individual basis, using the above points as guidance.

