5.1.2 Secondary endpoints

[figure not shown]
The key secondary endpoints to assess efficacy are as shown below. Throughout this CTP, the term "baseline" refers to the 4 week period prior to randomisation for the rate of symptomatic hypoglycaemic AEs with confirmed plasma glucose < 54 mg/dL (< 3.0 mmol/L) and/or severe hypoglycaemic AEs and the 2 week placebo run-in period for the mean daily insulin requirement.

- Incidence rate of symptomatic hypoglycaemic AEs with confirmed plasma glucose < 54 mg/dL (< 3.0 mmol/L) and/or severe hypoglycaemic AEs per patient-year from Week 5 to Week 26
 - o severe hypoglycaemia is defined as an event requiring the assistance of another person to actively administer carbohydrate, glucagon or other corrective actions. Plasma glucose concentrations may not be available during an event, but neurological recovery following the return of plasma glucose to normal is considered sufficient evidence that the event was induced by a low plasma glucose concentration (see Section 5.3.5.2)
 - The rate will be calculated from Day 29 (start of Week 5) up to Day 183 (end of Week 26 + 1 day) or date of last study medication intake + 1 day inclusive, whichever occurs first
- Incidence rate of symptomatic hypoglycaemic AEs with confirmed plasma glucose < 54 mg/dL (< 3.0 mmol/L) and/or severe hypoglycaemic AEs (see Section 5.3.5.2) per patient-year from Week 1 to Week 26
 - the rate will be calculated from the date of first study medication intake up to Day 183 (end of Week 26 + 1 day) or date of last study medication intake + 1 day inclusive, whichever occurs first
- Change from baseline in body weight (kg) after 26 weeks
- Change from baseline in total daily insulin dose (TDID), U/kg, after 26 weeks
- Change from baseline in systolic blood pressure (SBP) after 26 weeks
- Change from baseline in diastolic blood pressure (DBP) after 26 weeks

Trial Protocol Version 2.0

Page 46 of 122

Proprietary confidential information © 2016 Boehringer Ingelheim International GmbH or one or more of its affiliated companies

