6 GENERAL ANALYSIS DEFINITION

6.1 TREATMENTS

There will be six treatment phases in this trial: screening, T1DM therapy optimisation, placebo run-in, study treatment phase (with either BI-drug or matching placebo), post-treatment and post-study, as follows.

- The screening period starts from the date of informed consent and ends on the day before the start date of the T1DM therapy optimisation period.
- The T1DM therapy optimisation period begins with the start date of the insulin therapy optimisation visit (Visit 2) up to the day before the date of first administration of placebo run-in medication (inclusive).
- The placebo run-in period begins from the date of first administration of placebo run-in medication up to the day before the date of first administration of randomised study medication (inclusive).
- The on-treatment period begins from the date of first administration of study medication up to last intake of study drug + X days (inclusive) [see definition of X in [Table 6.7: 1](#)].
- The post-treatment period begins from the last intake of study drug + X days + 1 day up to the last contact date (inclusive). The last contact date is defined as the maximum of (trial completion date, and [last study drug intake + X days + 1 day]).
- The post-study period begins from the last contact date +1 day and ends at trial database lock date.

For efficacy and safety analyses, measurements will still be considered on-treatment during a follow-up period (X days) specific to each parameter. These follow-up periods are defined in Table 6.7: 1.

The efficacy analyses will follow the intention-to-treat (ITT) principle in assigning patients to treatment groups, i.e. patients will be analysed as randomised.

Safety analyses will assign patients to the treatment group as randomised.

If a patient erroneously receives the wrong trial drug, the patient will be analysed as randomised. In addition, AEs with an onset during the time of the incorrect study treatment will be tabulated and listed separately.

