7.5 SECONDARY ENDPOINTS

7.5.1 Key secondary endpoints

7.5.1.1 Rate of symptomatic hypoglycaemic AEs with confirmed plasma glucose <54 mg/dL and/or severe hypoglycaemic events confirmed by adjudication

[figure not shown]
Confirmatory analysis

The analysis of the rate of symptomatic hypoglycaemic AEs with confirmed plasma glucose <54 mg/dL and/or severe hypoglycaemic events confirmed by adjudication will utilise a negative binomial model, with terms for treatment, continuous baseline rate, continuous baseline HbA1c, continuous baseline eGFR and pre-existing insulin therapy as fixed effects and log(time at risk) as an offset. The results will be presented as a rate per patient-year. This analysis will be performed on the FAS (OC).

The baseline rate of symptomatic hypoglycaemic AEs with confirmed plasma glucose < 54 mg/dL and/or severe hypoglycaemic events confirmed by adjudication will be calculated based on the event rate during the 4 weeks prior to randomisation, see [Section 6.7](#).

The analysis of the rate from Week 5 to Week 26 will include all on-treatment events from the start of Week 5 (Day 29) until one day after treatment stop date. This period will also define the time at risk.

The analysis of the rate from Week 1 to Week 26 will include all on-treatment events from the date of first study drug intake until one day after treatment stop date. This period will also define the time at risk.

[REDACTED]

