A second frequency analysis will be created and will display the characteristics of ketoacidosis for patients with CEC certain ketoacidosis. These characteristics will include outcome, severity of the worst episode, time to onset of first episode, and lowest blood pH. This analysis will be successively repeated for ketoacidosis endpoints considered by the CEC as potential, as well as for ketoacidosis endpoints considered by the CEC as certain or potential.

Time to onset of the first CEC certain ketoacidosis event will be analysed by Kaplan-Meier estimates. The onset date determined by the adjudication committee will be used as date of event. The time to the occurrence of the event will be computed as date of the event minus date of first drug intake plus one day.

The Kaplan-Meier graph will present data up to the end of the treatment period.

Patient without an event will be considered censored at the date of the last trial drug intake plus seven day.

A log-rank test will be then computed to test the equality of the survival curves.

The Kaplan-Meier analysis and the log-rank test will then be performed for CEC certain or potential ketoacidosis event.

Frequency of patients with CEC certain ketoacidosis (and respectively CEC potential ketoacidosis) will be planned by preferred term from the specified trigger search terms for DKA.

- Analysis of frequency of ketoacidosis episodes

An overview table will first summarize the results of the CEC adjudication committee on ketoacidosis episodes by worst severity.

The CEC certain ketoacidosis episodes will be tabulated by treatment and characteristics of ketoacidosis (e.g. outcome, severity, pre-existing factors, blood pH).

When appropriate, the number of episodes per 100 patient-years will be calculated in addition to the number of episodes according to the following formula:

$100 * (\text{number of ketoacidosis events} / \text{time at risk [patient-years]})$ to report a diabetic ketoacidosis event)

Where time at risk [patient-years] is calculated as time from first administration of study drug until last administration of study drug + 7 days, summed up over all patients per treatment group, and divided by 365.25.

The same ketoacidosis episode analysis will be presented for CEC potential ketoacidosis, as well as for CEC certain or potential ketoacidosis.

- Other ketoacidosis endpoints

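### For patients lost to follow-up with no recorded drug stop date, the visible SAP text counts weeks with little or no event ascertainment as event-free time at risk

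*SAP*

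**What the plan says.** SAP 6.6.3 introduces its stop-date rules with "As a general rule a missing drug stop date will be imputed according to the following principles". For a patient lost to follow-up, "it should be the date of the last visit + the longest treatment duration based on drug supply + 1 day". A documented end-of-treatment visit, a partial date and a death each have their own rule, and anything else goes to the trial team case by case.

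SAP 7.5.1.1 counts events for the confirmatory Week 5 to 26 hypoglycaemia rate "from the start of Week 5 (Day 29) until one day after treatment stop date" and adds: "This period will also define the time at risk". The log of that time is the offset of the negative binomial model. The Week 1 to 26 rate works the same way from first intake.

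SAP 7.8.1.4 takes the denominator for ketoacidosis episodes as "time from first administration of study drug until last administration of study drug + 7 days". For the Kaplan-Meier analysis, "Patient without an event will be considered censored at the date of the last trial drug intake plus seven day". Severe hypoglycaemia follows the same scheme with one day in place of seven.

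Two other passages bear on this. Protocol 5.1.2 runs both key secondary rates "up to Day 183 (end of Week 26 + 1 day) or date of last study medication intake + 1 day inclusive, whichever occurs first". Visible SAP 7.5.1.1 does not repeat that cap, but SAP section 4 lists no departure from it. SAP 6.1 defines the last contact date as the later of trial completion and last intake plus the follow-up days plus one, so an imputed stop date can itself set it.

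**The concern.** The stop date does two jobs. When it labels a reported event as on-treatment, a late date is the cautious choice. When it measures exposure, a late date adds person-time during which the trial was hardly watching the patient. Hypoglycaemia rates rest on adverse event reports (Protocol 5.3.5.1), and a lost patient produces few of these. The added weeks enter the denominator almost empty. In effect zeros are imputed, although Protocol 7.5 says this endpoint is analysed from the available on-treatment data without imputation.

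The rates matter. Within each of the 10 mg and 25 mg branches, the two hypoglycaemia rates receive nine-tenths of the key secondary alpha (Protocol 7.2). Ketoacidosis and severe hypoglycaemia are adverse events of special interest with log-rank tests. Rates would be diluted in every arm, and comparisons would be distorted if loss were unequal.

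**Working it through.** The documents give no power or precision figure for these rates, so there is none to reproduce. The HbA1c sample size is not affected.

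**Inputs**
- Double-blind drug is dispensed at Visits 6, 8, 9 and 10 (Protocol Flow Chart and 4.1.4). Visits 8, 9, 10 and 11 EOT fall on Days 29, 85, 127 and 183. Supply from Visits 8, 9 and 10 therefore covers 56, 42 and 56 days.
- Reserve tablets are given, but the amount is not stated (Protocol 4.1.6). Assumed: 0 or 7 days.
- Full Week 5 to 26 window: Day 29 to Day 183, which is 183 − 29 + 1 = 155 days.
- Share lost: not given. Assumed: 1%, 2%, 5% or 10%, spread evenly over Visits 8 to 10.

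**Per patient**

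End of time at risk = last visit day + supply days + reserve + 1 (imputation) + 1 (hypoglycaemia follow-up). Credited days = end − 29 + 1. Observed days = last visit day − 29 + 1.

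| Lost after | End of time at risk, no reserve | Credited | Observed | Unobserved | Unobserved with 7-day reserve |
|---|---|---|---|---|---|
| Visit 8 | 29 + 56 + 2 = Day 87 | 59 | 1 | 58 | 65 |
| Visit 9 | 85 + 42 + 2 = Day 129 | 101 | 57 | 44 | 51 |
| Visit 10 | 127 + 56 + 2 = Day 185, capped at 183 | 155 | 99 | 56 | 56 |

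Without the Day 183 cap, the Visit 10 row would be 58 of 157. If the longest supply is read as 56 days whatever the visit, the Visit 9 row becomes 58 of 115.

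For ketoacidosis the follow-up is 7 days and the protocol's Day 183 cap does not apply. Time at risk then runs past the last visit by 56 + 1 + 7 = 64 days after Visit 8 or 10, and by 42 + 1 + 7 = 50 days after Visit 9.

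**Per arm, Week 5 to 26, no reserve, cap applied**

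Mean observed days per lost patient = (1 + 57 + 99)/3 = 52.33. Mean credited days = (59 + 101 + 155)/3 = 105. For lost share q, the crude rate is multiplied by

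[(1 − q) × 155 + q × 52.33] / [(1 − q) × 155 + q × 105].

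- q = 1%: 153.97/154.50 = 0.997
- q = 2%: 152.95/154.00 = 0.993
- q = 5%: 149.87/152.50 = 0.983
- q = 10%: 144.73/150.00 = 0.965

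**Rate ratio, active to placebo**
- 5% lost in both arms: 1.000
- 5% active, 2% placebo: 0.9827/0.9932 = 0.990
- 10% active, 2% placebo: 0.9649/0.9932 = 0.972

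These are pooled person-time figures. The negative binomial model weights patients somewhat differently.

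**The case against.** A reader might infer that the added time can contain no event at all. The documents do not support that. Protocol 5.3.7 asks investigators to report serious events and events of special interest learned of after the last per-protocol contact, if they consider them relevant. Ketoacidosis and severe hypoglycaemia are events of special interest. E-diary entries also reach a vendor server without a visit (Protocol 5.2.3). Ascertainment is reduced, not impossible.

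A reader might also infer that every lost patient adds up to eight weeks or more. The rule needs both a missing stop date and loss to follow-up. Early discontinuers are asked for an end-of-treatment visit and continued follow-up. The Visit 9 supply is shorter, and the Day 183 cap limits late losses. A patient lost before Visit 8 would normally lack an on-treatment HbA1c, fall outside the FAS and add nothing to the confirmatory rates.

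Nor do the documents show a bias in favour of empagliflozin. They give no loss rates, and equal loss leaves the crude rate ratio unchanged.

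A further fair point is that the SAP uses one window for events and exposure. Shortening exposure alone while still counting late-reported events would bias rates upwards. Any fix must keep the two matched.

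Finally, part of SAP 7.5.1 is redacted, and SAP 5.4.6, 5.4.7 and 9.3 are not shown. They may already contain a limiting rule. All these points stand. They narrow the concern but do not remove it, because nothing visible ends time at risk at the last real observation.

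**Conclusion.** The point holds as a minor one, on the visible text. Applied as written, the rule credits 44 to 58 largely unobserved days per affected patient in the Week 5 to 26 window without reserve supply. It understates an arm's crude rate by about 0.3%, 0.7% or 1.8% at an assumed 1%, 2% or 5% lost. The ratio shifts only with differential loss, by about 1% at 5% against 2%. These sizes rest on the assumed loss rates, an even spread of losses over Visits 8 to 10, no reserve, the Day 183 cap, and treating the last visit as the end of observation. Diary data after that visit would make the effect smaller. The sizes were not worked out for the ketoacidosis rates or the Kaplan-Meier curves, where the mechanism is the same.

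**What to change.** For the hypoglycaemia and ketoacidosis rates and the Kaplan-Meier analyses, end both event counting and time at risk at the earliest of:
- drug stop date plus the endpoint's follow-up days (1 or 7);
- Day 183, for the two key secondary rates, restated in SAP 7.5.1.1;
- the last date of actual observation, meaning the last visit, site contact or e-diary entry.

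State that this last date is not the last contact date of SAP 6.1, which the imputed stop date can set. Keep the imputed stop date for assigning adverse events to treatment. Report events of special interest learned of after the last observation in the adverse event tables or in a sensitivity analysis.

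The cost is a short SAP paragraph and some programming. Visit and diary dates are already collected, and no trial procedure changes. The small downside is that a few late-reported events leave the rate numerator. If a section not shown already sets such a limit, a cross-reference is enough.

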6.7 BASELINE, TIME WINDOW, AND CALCULATED VISITS

With regard to efficacy and safety endpoints, the term "baseline" refers to the last observed measurement prior to administration of any randomised study medication. For specific endpoints, baseline definitions are as follows:

Serum beta-hydroxybutyrate (BHB)

- Serum BHB sampled at the site and analysed at the central laboratory

Baseline will be defined as the fasted measurement observed at Visit 6, before first drug intake.

- Capillary patient self-measured BHB via the ketone meter and reported in the diary

For the analysis on morning or daily measurements (see [Section 7.8.2.5](#)), baseline will be defined as the mean of morning or daily measurements reported during the run-in period, respectively (Visit 5 to Visit 6, including the day of first administration of trial drug).

[REDACTED]

Hypoglycaemia rate

The event rate of hypoglycaemia (using the respective endpoint definition) during the 4 weeks prior to randomisation (from Day -28 up to Day -1). Collapsing will be performed as per the rules in Sections [5.4.6.3](#) and [5.4.7](#). Rates will be presented per 30 days and also per patient year.

Insulin dose (total daily, total daily basal or total daily bolus)

Mean daily insulin requirement during the run-in period (Visit 5 to Visit 6, excluding day of randomisation). If < 4 days of valid insulin data is reported during the run-in period then the measurement will be considered missing. For data handling rules see [Section 5.4.6.2](#).

[REDACTED]

[REDACTED]

[REDACTED]

[REDACTED]

[REDACTED]

Table 6.7: 1 Endpoint specific follow-up period for the assignment to active treatment

Endpoint	Last day of assignment to treatment phase (days after study drug stop date)
Efficacy	
HbA _{1c}	7
FPG	1
MDG	1
CGM	*
Body weight	1
Blood pressure	1
Waist circumference	7
Insulin dose	0
Hypoglycaemia	1
UACR	1
Health economics and QoL	1
Safety	
Adverse events	7
Hypoglycaemia ^[1]	1
Hepatic injury ^[2]	30
Safety laboratory measurements	3
AST/ALT/TBL ^[3]	30
Pulse rate	1

*Refer to [Section 5.4.4](#) for the assignment of CGM measurements to the on-treatment period

[1] Refer to all hypoglycaemia analyses except the general hypoglycaemia AE analysis by SOC and PT.

[2] Refer to a sensitivity analysis including all hepatic injuries with an onset date up to 30 days after the study treatment stop (see Section 7.8.1.4).

[3] Refer to a sensitivity analysis on elevated liver enzymes, for which events with an onset date up to 30 days after the study treatment stop will be included in the analysis.

Measurements taken after the last intake of study drug and after the end of the endpoint specific follow-up period will be considered off-treatment values.

Efficacy, safety, [REDACTED] will be assigned to visits based on time windows around the planned visit dates. These time windows are defined based on the planned number of days after the date of first administration of study drug (see [Table 6.7: 2](#)).

Table 6.7: 2 Time windows for HbA1c measurements at scheduled visits after randomisation

Visit number	Visit label	Planned days	Time window (actual days on treatment)	
			Start	End ^A
6	Baseline	0	NA	1 ^B
8	Week 4	28	2	56
9	Week 12	84	57	105
10	Week 18	126	106	154
11	Week 26	182	155	Study drug stop date + X days

^A In case of premature discontinuation of the study drug an eEOT visit has to be performed. Measurements from the eEOT visit will be assigned to the appropriate visit according to the table. In this case the time window for the visit that includes the eEOT visit will end X days after the study drug stop date, including Day X. The definition of X is endpoint specific, cf. [Table 6.7: 1](#). Patients will then be asked to continue in the study according to the visit schedule. Off-treatment measurements will be assigned to visits in the same manner. No time window for optional visit is planned.

^B Only values taken prior to the start of treatment with randomised study drug can be considered baseline values. Time windows will be used for assignment of measurements to scheduled visits.

The mid-point between two visits defines the end of a time window, with the midpoint being included in the time window of the preceding visit. The end of the time window of the last on-treatment visit (end of treatment (EoT)) is endpoint dependent (cf. [Table 6.7: 1](#)). As endpoints are planned to be measured according to different visit schedules, this midpoint algorithm will be applied and the time windows modified accordingly.

For example, the time windows for the blood pressure endpoints have been detailed in [Table 6.7: 3](#).

Table 6.7: 3 Time windows for blood pressure measurements at scheduled visits after randomisation

Visit number	Visit label	Planned days	Time window (actual days on treatment)	
			Start	End ^A
6	Baseline	0	NA	1 ^B
7	Week 1	7	2	17
8	Week 4	28	18	56
9	Week 12	84	57	105
10	Week 18	126	106	154
11 EOT	Week 26/EoT	182	155	Study drug stop date + X days

^A In case of premature discontinuation of the study drug an eEOT visit has to be performed. Measurements from the eEOT visit will be assigned to the appropriate visit according to the table. In this case the time window for the visit that includes the eEOT visit will end X days after the study drug stop date, including Day X. The definition of X is endpoint specific, cf. [Table 6.7: 1](#). Patients will then be asked to continue in the study according to the visit schedule. Off-treatment measurements will be assigned to visits in the same manner. No time window for optional visit is planned.

^B Only values taken prior to the start of treatment with randomised study drug can be considered baseline values. Time windows will be used for assignment of measurements to scheduled visits.

For insulin endpoints, as data is available on an ongoing basis, a value will be derived using the 14 days prior to drug stop date and time windowing will be applied as outlined above based on the drug stop data. Only data from within the visit window will be used to derive the visit value.

value on the last day of drug intake, the value on the last day of drug intake is used as the value of the last visit.

For pre-treatment time points, data will be assigned to nominal visits. Unscheduled visits will only be considered if the data would otherwise be missing for that time point.

Data prior to randomisation will be based on nominal visits and time windowing will not be applied. For these time points, data from the scheduled visit will always be selected. Unscheduled visits will only be considered if no data from the scheduled visit is available. If no data from a scheduled visit is available and multiple unscheduled values are available for a visit, the first value will be selected.

For standard descriptive tables of laboratory parameters by visit (created by the BI standard macro XLAB2), in case of multiple measurements within a post-baseline time window for a visit, the worst value of these multiple measurements will be used for calculations.

Note: for LOCF imputation, the last observed on-treatment value will be carried forward, whether or not it was selected in the previous time window. Also for interpolation any valid values can be used, regardless of whether they were selected as visit values. For more details on LOCF refer to [Section 6.6](#).

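### The run-in baseline for self-measured capillary BHB takes in the day of the first randomised dose without a pre-dose limit, so post-dose readings can enter the daily baseline

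*SAP*

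**What the plan says.** For capillary BHB, SAP 6.7 states that "baseline will be defined as the mean of morning or daily measurements reported during the run-in period, respectively", and gives the window as "Visit 5 to Visit 6, including the day of first administration of trial drug". SAP 7.8.2.5 sends the reader back to 6.7 for this definition, and SAP 7.1.1 lists daily and morning capillary BHB in the baseline tables.

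Other rules in the SAP point the other way:

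- The opening of 6.7 confines baseline to the time before any randomised medication.
- Footnote B to Tables 6.7: 2 and 6.7: 3 says "Only values taken prior to the start of treatment with randomised study drug can be considered baseline values".
- SAP 6.1 runs the placebo run-in "up to the day before the date of first administration of randomised study medication (inclusive)", and then "The on-treatment period begins from the date of first administration of study medication".
- The serum BHB baseline, set out just above the capillary one, is a fasted Visit 6 value taken before the first dose.
- The insulin-dose baseline over the same run-in is "Visit 5 to Visit 6, excluding day of randomisation".

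**The concern.** The window is called the run-in period, yet it contains a day that SAP 6.1 places outside run-in. A programmer working from 6.1 and one working from the parenthesis in 6.7 would build different baselines.

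The difference can matter because Day 1 is partly a treated day. The Visit 6 dose is taken at the site during a morning visit (Protocol 4.1.4 and 6.1), and empagliflozin peaks at about 1.5 hours (Protocol 1.2.2.1). Ketones may be tested at any hour if symptoms suggest DKA (Protocol 5.3.2.2). A reading taken after the dose would be averaged into the baseline. If BHB had already risen, the baseline would rise with it, and a later increase judged against that baseline would look smaller. That is the unfavourable direction for a safety measure linked to DKA.

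**Working it through.** The documents give no figure for this point, so there is nothing to reproduce. The size follows from the weight that post-dose readings carry in the baseline mean.

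**Inputs from the documents**
- Run-in: Day -14 to Day -1, ideally 14 days (Protocol Flow Chart, footnote A).
- Recommended home ketone testing: before breakfast, about once daily in run-in and at least 2 to 3 times a week throughout (Protocol 5.3.2.2).
- Day 1: patients are told not to take trial medication before visits (Protocol 4.1.4), and Visit 6 assessments precede randomisation and the first dose (Protocol 6.2.2.1).
- Minimum data: for insulin, "If < 4 days of valid insulin data is reported during the run-in period then the measurement will be considered missing". No such rule is visible for capillary BHB.

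**Assumptions, not in the documents**
- One reading per tested run-in day (R readings), one pre-dose reading on Day 1, and k post-dose readings on Day 1, with k from 0 to 4.
- A mean post-dose rise on Day 1 of d = 0.05 to 0.3 mmol/L.

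**Formulas**
- Shift in baseline = w × d, where w is the weight of the post-dose readings.
- All readings pooled: w = k / (R + 1 + k).
- Mean of daily means: w = [k / (k + 1)] / (R + 1).

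The public SAP does not show which averaging method applies, so both are given.

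| Case | Pooled | Mean of daily means |
|---|---|---|
| k = 0, any R (usual morning endpoint) | 0% | 0% |
| R = 14, k = 1 | 1/16 = 6.3% | 0.5/15 = 3.3% |
| R = 14, k = 4 | 4/19 = 21.1% | 0.8/15 = 5.3% |
| R = 6 (3 per week), k = 1 | 1/8 = 12.5% | 0.5/7 = 7.1% |
| R = 4 (2 per week), k = 1 | 1/6 = 16.7% | 0.5/5 = 10.0% |
| R = 0, k = 1 | 1/2 = 50% | 0.5/1 = 50% |

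**In mmol/L**
- At w = 1/16: 0.05/16 = 0.003 to 0.3/16 = 0.019.
- At w = 4/19: 0.05 × 4/19 = 0.011 to 0.3 × 4/19 = 0.063.

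For scale, the lower category limits for serum BHB in SAP 7.8.2.5 are 0.6 and 1.5 mmol/L.

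**The case against.** The best defence is that 6.7 lists endpoint-specific baselines after its general rule, so the capillary definition may be a deliberate exception. Including Day 1 sensibly keeps the last before-breakfast reading, which is normally pre-dose. For the morning endpoint this largely stands. It does not rescue the daily endpoint, because nothing visible limits Day 1 to such readings, and the exception still calls a day run-in that 6.1 does not.

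Readers might also draw stronger conclusions that the documents do not support:

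- **That the rise on empagliflozin is understated as a matter of fact.** This needs post-dose Day 1 readings, a same-day rise and a comparison with baseline. SAP 7.8.2.5 plans period averages for capillary BHB and names change from baseline only for serum BHB.
- **That Day 1's share of the days, 1/15 = 6.7%, is the bias.** With one before-breakfast reading a day, the Day 1 value is pre-dose and the bias is 0%.
- **That only the active arms are affected.** This holds for the drug effect. The Day 1 insulin advice in Protocol 4.2.1 applies to all randomised patients, so insulin-related ketone changes could enter the placebo baseline too.
- **That patients will be placed in the wrong baseline BHB category.** Categories are referred to SAP 6.4, which is not visible, and the limits in 7.8.2.5 are for serum BHB.
- **That the same readings count in both baseline and Week 1.** This is possible under 6.1, but the visible text does not give the day limits of Week 1 for BHB.

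SAP 5.4.6.1, on ketone readings, is also not visible. It may define morning readings or settle the averaging.

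**Conclusion.** The contradiction is real and does not depend on the size of the effect. As written, SAP 6.7 allows post-dose readings into a baseline that its own general rule, footnote B and SAP 6.1 reserve for pre-dose values. The consequence is confined mainly to the daily capillary endpoint and its baseline table.

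The likely effect is small: nil if all readings are pre-dose, and about 3% to 6% of the Day 1 rise with near-daily run-in testing and one post-dose reading. It grows with sparse testing or repeated post-dose tests, and no minimum-data rule is visible to limit it. These figures rest on the assumed reading counts, and the mmol/L values on the assumed rises.

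The verdict reads trial drug in the capillary definition as randomised drug, as SAP 7.8.4 uses the term. If it meant run-in placebo, the point would fall. The serum BHB, ketosis-episode and adjudicated ketoacidosis analyses do not use this baseline.

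**What to change.** In SAP 6.7, define both the morning and the daily capillary BHB baselines as the mean of readings from Visit 5 up to the first randomised dose. Count later Day 1 readings as on-treatment only, in line with 6.1. The dosing time at visits is already recorded in the eCRF (Protocol 4.1.4), and SAP 6.6.3 already imputes a missing first-dose time as 08:00. If reading times are not usable, end the daily baseline on Day -1.

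The cost is one sentence and a date-and-time filter. At most one reading day is lost from a run-in of about 14 days.
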